2. Understand the post-discharge treatment patterns (including persistence, switch, and discontinuation) among patients who started on apixaban or warfarin in the hospital

The secondary objective is to:

3. Assess recurrent VTE, major bleeding, and clinically relevant non-major (CRNM) bleeding among patients who continue on apixaban or warfarin in the outpatient setting while persistent on index therapy

Study design

A retrospective database analysis will be conducted among patients hospitalized with a primary diagnosis of VTE. This study will utilize linked data from IQVIA's hospital charge master data (CDM), professional fee claims (Dx) and prescription claims (LRx) from 01 July 2017 through 31 December 2022 or the latest available data at the time of extraction (i.e., the *study period*), including 6-month pre-hospitalization period (starting the day before the admit date of hospitalization and a minimum 1-month post-hospitalization (starting a day after discharge date of hospitalization) period. The first apixaban or warfarin treatment during the index hospitalization will be flagged. Following discharge, patients who continue apixaban or warfarin, respectively, in the outpatient setting (with outpatient treatment claim occurring on or within 30-days following the discharge date) will be identified. The date of the first apixaban or warfarin claim will serve as the treatment index date. The baseline period will be 6 months prior to the treatment index.

Population

The study cohorts will be identified during the selection window from 01 January 2018 to 30 November 2022. Based on the treatment (apixaban or warfarin) received during the VTE hospitalization, patients will be classified into apixaban and warfarin cohorts. Patients will be required to have medical and pharmacy activity during the 6 month pre-hospitalization period and 1-month post-hospitalization period i.e. post-discharge. Following discharge, patients will be indexed to either apixaban or warfarin based on the first observed outpatient pharmacy claim for the respective therapy, and will have a 6-month baseline period prior to the treatment index date and a variable follow-up period after the treatment index date. Treatment patterns and clinical outcomes will be evaluated during the variable follow-up period.

Variables

Exposures and explanatory variables on the treatment index date and 6-months prior to the treatment index period (which includes the hospitalization)

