9.1. Study period and study design

The analysis will be conducted using data from 01 July 2017 through 31 December 2022 or the latest available data at the time of extraction (i.e., the *study period*). Figure 1 illustrates the study schematic for this project. The study cohorts will be identified during a selection window from 01 January 2018 to 30 November 2022. The date of the first treatment with apixaban or warfarin during the hospitalization will be flagged. Based on this treatment during the VTE hospitalization, patients will be classified into the apixaban and warfarin cohorts. Patients will be required to have medical and pharmacy activity during the 6 months prior to the admit date of the hospitalization (pre hospitalization period) and 1-month (minimum) from the discharge date of the hospitalization (post hospitalization period). The date of the first outpatient prescription for apixaban or warfarin on or within 30 days after discharge date from the hospitalization will be termed as ‘treatment index date’.

Figure 1. Study Period

*Latest available data at the time of extraction will be utilized for this study

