9.1.1. Inclusion criteria

Patients must meet all of the following inclusion criteria to be eligible for inclusion in the study:

1. Patients with an inpatient hospitalization with admit date and discharge date between 01 January 2018 and 30 November 2022 (selection window) in CDM with a primary diagnosis of VTE

Note: The admit date of the first hospitalization with primary diagnosis of VTE during the selection window will be flagged. Only patients with overnight stays with discharge date after the admit date (to confirm inpatient stay with overnight admission) will be included in the study.

Note: Number of patients who died during hospitalization (identified from discharge disposition measure) will be reported and these patients will be excluded from the study.

2. With evidence of receiving apixaban or warfarin during the hospitalization

Note: The date of the record with first apixaban or warfarin administration during the hospitalization will be flagged as the start of apixaban or warfarin treatment. Patients will be assigned to the apixaban or warfarin cohort based on this treatment received during hospitalization.

3. With linkage to LRx between 01 July 2017 and 31 December 2022 (i.e. study period)
4. With linkage to Dx during the study period
5. With activity in the 6 months prior to the admit date of hospitalization, defined as ≥ 1 claim in Dx and ≥ 1 prescription claim in LRx (pre hospitalization period)
6. With activity in the 1-month after the discharge date of hospitalization, defined as ≥ 1 claim in Dx and ≥ 1 prescription claim in LRx (variable post hospitalization period)
Note: Patients will have a minimum 1-month post discharge period (to capture outpatient treatment)
7. With age ≥ 18 years on apixaban or warfarin administration date during index hospitalization

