9.2. Variables

[figure not shown]
From the final sample, the following measures will be reported (Figure 2):

1. Patients with a claim for the respective treatment (apixaban for apixaban cohort or warfarin for warfarin cohort; using NDC from LRx) as their first post-discharge outpatient treatment (on or within 30 days following discharge i.e. discharge date or ≤ 30 days after discharge date) (n, %). These patients will comprise the analytic cohort for outcomes assessment.

- a. The date of the first post-discharge outpatient prescription claim in LRx (apixaban or warfarin) will be defined as the ‘treatment index date’ for patients in both cohorts respectively.
 - b. Patients will be required to have pharmacy stability during the 6-month period preceding the treatment index date, defined as consistent reporting of data in each month from the pharmacy associated with the treatment index date in LRx to ensure continuous visibility within LRx. The number of patients excluded due to lack of stability will be reported (n, %)
 - c. Patients with recurrent VTE, major bleeding, or CRNM bleeding between the discharge date and the treatment index date will be excluded. The number of patients excluded due to these reasons will be reported (n, %).
 - d. Patients will be followed from the treatment index date until the earliest of last prescription, last patient medical claim, end of pharmacy stability, or end of study period using the Dx/Rx databases.
2. Patients with OAC (warfarin, apixaban, rivaroxaban, dabigatran, or edoxaban) other than the respective inpatient treatment as their first outpatient prescription claim (on discharge date or within 30 days of discharge) (NDC codes from LRx; n, %). These patients will be captured as having switched from inpatient therapy and will not be further evaluated for outcomes.
 3. Patients with no post-discharge outpatient prescription claim for any OAC (on or within 30 days of discharge) (NDC from LRx; n, %)

All study outcomes will be evaluated for the apixaban and warfarin cohorts.

Figure 2. Study Flow

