9.2.1. Baseline Measures

Baseline demographic, hospitalization and clinical characteristics will be assessed for the apixaban and warfarin cohorts, specifically among patients with their first outpatient index prescription (i.e. treatment index date) and with pharmacy stability. Demographic features will be measured on the patient’s treatment index date. Clinical characteristics will be assessed during the 6-months prior to the treatment-index date. Index hospitalization characteristics will also be assessed and reported for the apixaban and warfarin cohorts.

Baseline demographic characteristics (using LRx data)

- Age (years; mean, standard deviation [SD], median, interquartile range (IQR), min, max)
- Age group (18-34, 35-44, 45-54, 55-64, ≥65 years; n, %)
- Gender (male, female; n, %)
- Payer type (Third party, Medicaid, Medicare, Medicare part D, cash, other; n, %)
- Index date year (2018, 2019, 2020, 2021, 2022; n, %)

090177e19cc79c7fApproved\Approved On: 03-Mar-2023 00:48 (GMT)

- Follow-up duration (mean, SD, median, IQR, min, max)

Hospitalization characteristics (using CDM data)

- Hospital geographic region (Northeast, Midwest, South, West)
- Number of hospital beds (1-99 beds, 100-199 beds, 200-299 beds, 300-499 beds, 500+ beds)
- Hospital location (Rural, Urban)
- Teaching status (Teaching, Non-teaching)
- Admitting source (ER, referral and transfer, routine admission, other, unspecified)
- Discharge disposition (Alive – Home, Left Against Medical Advice or Discontinued Care [LAMA], Transferred – Long Term Care, Transferred – Other Institution, Transferred – Short-Term Hospital, Unknown/Other)
- Index VTE type (DVT only, PE only, DVT and PE; n, %).
- VTE etiology: (Provoked: VTE preceded by hormone therapy, fracture/trauma involving lower extremities, pelvic/orthopedic surgery, or hospitalization for any reason for ≥ 3 days during 3 months prior to index VTE event. Unprovoked: VTE events not classified as provoked)

Baseline clinical characteristics

- Prescribing provider specialty associated with the treatment index prescription in LRx (primary care [general practice/family practice/internal medicine/physician assistant/nurse practitioner], cardiologist, other, unknown; n, %) (Frequency table will be provided with details on provider specialty counts within ‘other’ category)
- Charlson Comorbidity Index (CCI, Dartmouth-Manitoba adaptation; mean, SD, median, IQR, min, max)
- CCI (categorical [0-1, 2, 3, 4+]); n, %)

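### The LRx half of inclusion criterion 6 selects on a fill in the same month as the 30-day continue / switch / no-OAC split, and the two windows disagree about the discharge day

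*Combined protocol and SAP*

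**What the plan says.** Criterion 6 in Section 9.1.1 requires "activity in the 1-month after the discharge date of hospitalization, defined as ≥ 1 claim in Dx and ≥ 1 prescription claim in LRx". Any drug satisfies the LRx half.

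Section 9.2 starts where eligibility ends: "From the final sample, the following measures will be reported". It forms three groups from LRx: first OAC claim for the inpatient drug, first OAC claim for another OAC, and "Patients with no post-discharge outpatient prescription claim for any OAC (on or within 30 days of discharge". The first group, whose window is "on or within 30 days following discharge i.e. discharge date or ≤ 30 days after discharge date", becomes the analytic cohort for outcomes.

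The activity window behind criterion 6 is worded in three ways:
- Abstract, study design: "minimum 1-month post-hospitalization (starting a day after discharge date of hospitalization) period".
- Section 9.1: "1-month (minimum) from the discharge date of the hospitalization (post hospitalization period", which can be read with or without the discharge day.
- Criterion 6 itself: after the discharge date.

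On reporting, the plan promises counts for in-hospital deaths (Section 9.1.1), for patients given both study drugs in hospital (Section 9.1.2), and for pharmacy-stability and early-event exclusions (Section 9.2). Section 9.1.2 also plans a preliminary attrition table for the sponsors, without listing its rows. Discharge disposition is tabulated in Section 9.2.1, "specifically among patients with their first outpatient index prescription (i.e. treatment index date) and with pharmacy stability". Section 9.8 explains that activity rules stand in for continuous enrollment, which these databases cannot show.

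**The concern.** An OAC fill on days 1 to 30 meets the LRx half automatically. A patient without an OAC fill stays only if some other drug was dispensed. Eligibility is therefore partly conditioned on the quantity being measured, and patients with no fill at all leave the denominator before non-filling is counted.

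Separately, the window wording lets two programmers build different cohorts from the same text.

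The split answers part of objective 2 (Section 8), which concerns patients who started apixaban or warfarin in hospital. Post-discharge continuity is a listed outcome in the Abstract, and the rationale is that many such patients fill no anticoagulant after discharge. A reader of the results would know the stated denominator. The reader would not know how many patients the LRx half removed, or whether they resemble non-fillers or patients who simply could not be seen.

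**Working it through.** The plan states no figure for this split, so there is nothing to reproduce. All shares below are assumptions.

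**Step 1. Who is kept, setting the sections side by side** (LRx half only).

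| LRx claims after discharge | Class in 9.2 | Window includes discharge day | Window starts day after |
|---|---|---|---|
| Index drug, days 1–30 | Continuer | kept | kept |
| Index drug on discharge day, nothing later | Continuer | kept | removed |
| Other OAC on discharge day, nothing later | Switcher | kept | removed |
| Non-OAC drug only, days 1–30 | No OAC | kept | kept |
| Non-OAC drug on discharge day, nothing later | No OAC | kept | removed |
| No claim of any drug | No OAC | removed | removed |

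The second row is the direct contradiction. Those patients are also lost from the outcome cohort.

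**Step 2. Window includes the discharge day.** Suppose that without the LRx half the observed split is C = 70% continue, 5% switch, Z = 25% no OAC. Let f0 be the share with no LRx claim. Continuation = C/(1 − f0); no OAC = (Z − f0)/(1 − f0).

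| f0 | Share of no-OAC group removed (f0/Z) | Continuation | No OAC |
|---|---|---|---|
| 2% | 8% | 0.70/0.98 = 71.4% | 0.23/0.98 = 23.5% |
| 5% | 20% | 0.70/0.95 = 73.7% | 0.20/0.95 = 21.1% |
| 10% | 40% | 0.70/0.90 = 77.8% | 0.15/0.90 = 16.7% |

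This is the shift relative to what LRx shows, not the distance from true continuation.

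**Step 3. Window starts the day after.** Let d be the share whose only LRx claim is the index drug on the discharge day, and n the share of switchers and no-OAC patients removed for the same reason. Continuation = (C − d)/(1 − f0 − d − n). It equals C when d = (f0 + n)·C/(1 − C). With f0 = 5%:

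| d | Continuation, n = 0 | Continuation, n = 2% | Continuers lost from outcome cohort (d/C) |
|---|---|---|---|
| 2% | 73.1% | 74.7% | 2.9% |
| 5% | 72.2% | 73.9% | 7.1% |
| 10% | 70.6% | 72.3% | 14.3% |
| 15% | 68.8% | 70.5% | 21.4% |

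Break-even d is 0.05 × 0.70/0.30 = 11.7% if n = 0, and 0.07 × 0.70/0.30 = 16.3% if n = 2%.

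**Step 4. Distance from the truth.** Now let 70% be true continuation and 25% true non-filling. Let u be the share unseen in LRx after discharge (independent of true status) and g the share of true non-fillers who fill no drug. The window includes the discharge day. Then f0 = u + (1 − u)Zg, the planned split gives C/(1 − Zg), and the split without the LRx half gives (1 − u)C.

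- Planned: 71.8%, 74.7%, 80.0% for g = 10%, 25%, 50%.
- Without the LRx half: 70.0%, 68.6%, 66.5%, 63.0% for u = 0%, 2%, 5%, 10%.
- The planned figure is nearer when u > Zg/(1 − Zg), that is 2.6%, 6.7%, 14.3% for the three values of g.

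The same f0 = 5% fits u = 5%, g = 0 (planned 70.0%, without 66.5%) and u = 0, g = 20% (planned 73.7%, without 70.0%). So f0 alone does not say which figure is nearer.

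**The case against.** The LRx half is a disclosed visibility rule. Sections 9.3 and 9.8 say that enrollment cannot be defined in open data and that proxies must be used. The denominator is stated, so the reported share is openly conditional. Section 9.3 gives LRx coverage of 92% for retail, 72% for mail and 76% for long-term care, and Section 9.8 gives 63% of retail pharmacies. None of these is u, because criterion 5 already requires an earlier LRx claim, but they show that unseen fills are a real problem. Without the LRx half, unseen fills, transfers to institutions and post-discharge deaths would all count as no OAC. This stands, and it is why the planned split should remain the main result.

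A reader might infer that the plan will not show the loss at all. The documents do not support that: the preliminary attrition table would normally have a row for criterion 6. What is missing is a commitment to show the LRx half separately, by cohort, in the final results. Disposition as planned cannot fill the gap, because it is tabulated only for patients already indexed and stable. Figures 1 and 2 were not in the text available for this check and should be looked at for a window start or a count.

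A reader might also infer that continuation is necessarily overstated, or that the error changes sign at d = 11.7%. Step 4 shows that the first depends on u and g. The second holds only if the day-after window removes no switcher and no no-OAC patient (n = 0). The documents give none of these quantities.

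**Conclusion.** The window conflict is wrong as written and needs no assumption: Section 9.2 counts a discharge-day fill that the Abstract and criterion 6 do not accept as activity. The selection on an LRx claim is real but serves a legitimate purpose. Reporting its size and one split without it would be a cheap improvement.

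The illustrative shift is 1.4 to 7.8 percentage points of continuation for f0 of 2% to 10%, on an assumed 70/5/25 split with the discharge day included. Neither the actual size nor the net direction can be told from the documents.

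The scope is narrow. OAC non-fillers with another fill stay in, so the no-OAC group is not emptied. It would also be too strong to read this as a bias in persistence, Kaplan-Meier or clinical outcomes generally. Those start from an index OAC fill and are touched only through the day-after wording, which drops continuers whose only LRx claim in the month was on the discharge day.

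**What to change.** 1. Word the activity window identically in the Abstract, Section 9.1 and criterion 6, including the discharge date and using the 30-day length of Section 9.2. If the Dx half shares that window, it too would accept a discharge-day claim; say whether that is intended.
2. Report in the final results the number failing only the LRx half of criterion 6, by cohort and discharge disposition.
3. Keep the planned split as the main result. Add one sensitivity split without the LRx half, all other criteria unchanged (criterion 5 and the Dx half retained, no added stability rule). Present the pair as a sensitivity range, not as bounds.
4. State in Section 9.8 that in the sensitivity version unseen fills, post-discharge deaths and transfers count as no OAC, and that both versions remain conditional on the Dx half.

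The cost is one wording change, one cross-tabulated count using a variable already in CDM, one rerun of the split and a short limitations statement. The downside is a second figure beside the continuation share that is not a strict bound. A patient who fills the OAC at a non-reporting pharmacy and other drugs at a reporting one counts as no OAC in both versions.

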9.1.2. Exclusion criteria

Patients meeting any of the following criteria will be excluded from the study:

1. Patients with hospitalization with a primary diagnosis of VTE in the 6-month pre hospitalization period
2. Patients with any OAC administration other than apixaban for apixaban cohort (except warfarin use before apixaban) or warfarin for warfarin cohort during hospitalization

Note: Apixaban cohort patients will be allowed to have warfarin prior to apixaban administration. At this step, we will also report the number of patients that have both apixaban and warfarin use during the hospitalization.

3. Patients with unfractionated heparin or low molecular weight heparin (LMWH) administration after apixaban (for apixaban cohort) or warfarin (for warfarin cohort) administration during hospitalization.

Note: that unfractionated heparin or LMWH prior to apixaban or warfarin will be allowed.

4. With ≥ 1 claim/record with a diagnosis code for atrial fibrillation/flutter in Dx or CDM during the hospitalization and in the 6-month pre hospitalization period
5. With ≥ 1 claim with a procedure code for mechanical heart valve in Dx or CDM during the hospitalization and in the 6-month pre hospitalization period
6. With ≥ 1 claim with a procedure code for inferior vena cava filter in Dx or CDM during the study period
7. With ≥ 1 claim with a diagnosis code or procedure code of pregnancy in Dx or CDM during the study period
8. With use of OAC or PAC (in LRx or Dx) (unless prophylactic) during the 6-month pre-hospitalization period

Note: The OAC or PAC prescription claim will be considered prophylactic if duration of the prescription is ≤ 42 days AND the start date of OAC or PAC occurs within 2 days before or 7 days after knee/hip replacement surgery

OR

Start date of OAC or PAC occurred within 7 days after the admission of a hospitalization associated with 'medically ill' (primary discharge diagnosis; codes provided separately) AND with a ≥ 3 -day length of stay of the hospitalization.

9. With data quality issues (invalid/missing enrollment dates, gender and payer type)

A preliminary attrition table will be provided to the Alliance for review, at which time modifications to the inclusion and exclusion criteria may be considered.

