- Comorbidities of interest (ICD-10 diagnosis codes in Dx or CDM; n, %)
 - Acquired immune deficiency syndrome (AIDS)
 - Alcohol/drug abuse
 - Anemia
 - Cerebrovascular disease
 - Coronary heart disease/ischemic heart disease
 - Congestive heart failure
 - Chronic obstructive pulmonary disease (COPD)
 - Coronavirus disease 2019 (COVID-19)

090177e19cc79c7f\Approved\Approved On: 03-Mar-2023 00:48 (GMT)

- Dementia/Alzheimer's disease
- Dyspepsia or stomach discomfort
- Diabetes mellitus
- Hemiplegia/Paraplegia
- Hematologic disorders associated with bleeding (thrombocytopenia)
- Hyperlipidemia
- Hypertension
- Inflammatory bowel disease
- Liver/Gall bladder/Pancreatic disease
- Obesity
- Peptic ulcer
- Peripheral vascular disease
- Pneumonia
- Renal disease
- Rheumatologic disease
- Sleep apnea
- Spinal cord injury
- Thrombocytopenia
- Thrombophilia
- Varicose veins
- Procedures of interest (ICD-10 diagnosis or procedure codes, CPT Codes, HCPCS codes in Dx or CDM; n, %)
 - Orthopedic surgery
 - Central Venous Catheter
- Baseline bleeds (ICD-10 diagnosis or procedure codes, CPT Codes, HCPCS codes in Dx or CDM; n, %)
 - Gastrointestinal
 - Intracranial
 - Others
- History of falls (ICD-10 diagnosis codes in Dx or CDM; n, %)
- Fracture/trauma involving lower extremities (ICD-10 diagnosis codes in Dx or CDM; n, %)

- Medications of interest (NDC or HCPCS codes in LRx or Dx; n, %)
 - Angiotensin-converting enzyme (ACE) inhibitors/Angiotensin receptor blockers (ARB)
 - Antiarrhythmic agents
 - Antiplatelet agents
 - Aromatase inhibitors
 - Beta blockers
 - Erythropoiesis stimulating agents (ESA)
 - Gastroprotective agents
 - Nonsteroidal anti-inflammatory drugs (NSAID)
 - Selective estrogen receptor modulators (SERM)
 - Statins

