9.6. Data analysis

Descriptive statistics will be produced for all relevant study measures previously described, for the overall cohort and for each treatment (apixaban and warfarin). Categorical measures will be presented using frequency (number of patients [n]) and percentage (%) of total study patients observed in each category. Continuous and count variables will be presented as the mean, SD, median, minimum, maximum and IQR. As relevant, continuous variables will also be categorized into intervals. Univariate statistics will be calculated for each measure of interest. No comparisons will be made between the two cohorts..

Four multivariable regression models will be developed for this study. Cox proportional hazards models will be conducted to evaluate both the risk (expressed as hazard ratios with corresponding 95% confidence intervals) of discontinuing or switching from the index treatment as well as the risk of experiencing a clinical event (i.e., recurrent VTE, major bleeding, or CRNM bleeding).. The main effect variable will be the treatment cohort (apixaban vs. warfarin, with warfarin as the reference group). Covariates to be considered for inclusion into the models will include demographic and clinical characteristics of interest. A backward elimination of independent variables least associated with the dependent variable may be used. Clinically relevant covariates that are not retained during backward elimination may also be forced into the model. Collinearity among the variables of interest will be evaluated during model development.

Kaplan-Meier analyses will also be utilized to report the time to an event of interest (e.g., switch, discontinuation). Kaplan-Meier is a method for estimating the probability of the proportion of individuals remaining in the sample at a particular time from an initiation point. It takes into account patients lost or censored before the study endpoint. All analyses will be based on observed, not projected, data. Analyses will be conducted using SAS[®] Release 9.4 (SAS Institute Inc., Cary, NC), and the results will be reported in Excel tables.

Any major modifications of primary endpoint definitions (treatment patterns) or their analyses would be reflected in a protocol amendment.

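### Earlier VTE is only partly excluded and VTE history is not a listed baseline characteristic, so the Cox models do not plan to adjust for it

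*Combined protocol and SAP*

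**What the plan says.** **Exclusions (section 9.1.2).** Criterion 1 removes "Patients with hospitalization with a primary diagnosis of VTE in the 6-month pre hospitalization period". Criterion 8 removes patients "With use of OAC or PAC (in LRx or Dx) (unless prophylactic) during the 6-month pre-hospitalization period".

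**Choice of index stay (section 9.1.1, inclusion criterion 1, note).** "The admit date of the first hospitalization with primary diagnosis of VTE during the selection window will be flagged". The selection window opens on 01 January 2018.

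**Baseline variables (section 9.2.1).** "Clinical characteristics will be assessed during the 6-months prior to the treatment-index date", and the abstract describes this baseline as "6-months prior to the treatment index period (which includes the hospitalization"). The VTE-related items are "Index VTE type (DVT only, PE only, DVT and PE; n", %) and a provoked/unprovoked classification that does not use earlier VTE. The list headed "Comorbidities of interest (ICD-10 diagnosis codes in Dx or CDM; n", %) has 28 entries. Thrombophilia and varicose veins are among them; prior VTE, DVT or PE is not.

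**Models (section 9.6).** Treatment cohort is the main effect, with warfarin as reference. On adjustment the section says: "Covariates to be considered for inclusion into the models will include demographic and clinical characteristics of interest". Backward elimination may be used, and clinically relevant covariates that it drops may be put back.

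**The concern.** One of the clinical outcomes is *recurrent* VTE, yet the plan has no variable showing whether the index event was itself a recurrence. A previous VTE could plausibly influence the choice between apixaban and warfarin, the intended length of treatment, and the risk of another event. If it does, it confounds the hazard ratios for recurrent VTE (a secondary objective) and for discontinuation or switching (part of the main objectives). The tables would also combine first and repeat events without showing the split.

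Section 9.6 says that the cohorts will not be compared, but a Cox model whose main effect is apixaban versus warfarin yields a comparison that readers will use. Control of confounding therefore matters here.

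**Working it through.** The plan states no figure on this point, so there is none to reproduce. The check has three steps.

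**1. Who with an earlier VTE is still eligible?**

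| Rule | Removes | Leaves in |
|---|---|---|
| Criterion 1 | Primary-diagnosis VTE admission in the 6 months before admission | Older admissions; outpatient or secondary-diagnosis VTE |
| Criterion 8 | Non-prophylactic OAC or PAC use in the same 6 months | VTE whose treatment ended more than 6 months earlier, or with no anticoagulant claim in LRx or Dx |
| First-in-window rule | Any earlier primary-diagnosis VTE admission recorded in CDM since 01 January 2018 | Admissions before that date and outside the 6 months; admissions to hospitals outside CDM |

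Sections 9.3 and 9.8 both say that care at non-contributing hospitals is not visible.

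**2. How far back do the rules look for an earlier primary-diagnosis admission in CDM?** The look-back is the longer of 6 months (criterion 1) and the time since 01 January 2018 (first-in-window rule), with a month taken as 30.4375 days.

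| Index admission | First-in-window look-back (months) | Effective look-back (months) |
|---|---|---|
| 01 Jan 2018 | 0.0 | 6 |
| 01 Jul 2018 | 5.9 | 6 |
| 01 Jul 2020 | 30.0 | 30 |
| 29 Nov 2022 | 58.9 | about 59 |

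The look-back is therefore not a uniform 6 months; it grows with index date. Section 7 reports that apixaban use for VTE has risen strongly. If warfarin index dates therefore fall earlier in the window (an inference, not a stated fact), warfarin patients are screened over a shorter period, and residual history could differ between cohorts by design.

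**3. What could omission do to the recurrent VTE hazard ratio?** For an unadjusted binary confounder with prevalence pA (apixaban) and pW (warfarin) and relative risk RR for the outcome:

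bias factor = [1 + pA(RR − 1)] / [1 + pW(RR − 1)]

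The documents give none of these three inputs, so all the values below are assumptions.

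| RR | pA | pW | Calculation | Factor |
|---|---|---|---|---|
| 2.0 | 10% | 15% | 1.10 / 1.15 | 0.957 |
| 2.0 | 10% | 20% | 1.10 / 1.20 | 0.917 |
| 2.5 | 10% | 25% | 1.15 / 1.375 | 0.836 |
| 3.0 | 5% | 20% | 1.10 / 1.40 | 0.786 |
| 2.0 | 10% | 10% | 1.10 / 1.10 | 1.000 |
| 2.0 | 15% | 10% | 1.15 / 1.10 | 1.045 |

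The fourth row is a deliberately wide contrast. The last two rows show that the effect vanishes with equal prevalence and changes direction when history is commoner with apixaban. The formula treats history as independent of the covariates already in the model and the outcome as uncommon. It is not applied to discontinuation or switching.

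**The case against.** A reader might infer that earlier VTE is excluded only as a recent primary-diagnosis admission, and that the models cannot adjust for what remains. Neither reading holds. Criterion 8 also removes VTE under recent drug treatment, including VTE managed outside hospital, and the first-in-window rule extends the look-back for CDM admissions to as much as about 59 months. Section 9.6 describes the covariates in open terms, gives no closed list, and allows for clinical judgement.

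It can also be said that the size of any bias is wholly assumed. Thrombophilia and provoked/unprovoked etiology, both collected, may absorb part of the effect. Section 9.8 already limits the results to associations and names possible misclassification of newly treated patients. On this view, one more covariate is a matter of preference.

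Much of this stands, and it limits the point to what is not planned and to an unknown size. It does not remove the point. The provision for restoring a covariate concerns variables that were considered and then dropped; VTE history has no definition or code list, so there is nothing to restore. Section 9.8 does not mention unmeasured VTE history. The growing look-back narrows the gap unevenly over calendar time.

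**Conclusion.** The concern holds as a minor omission. Earlier VTE is partly excluded, what remains is not measured, and the Cox models have no planned adjustment for it. The stronger statement, that adjustment is impossible, is not supported by section 9.6.

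The size and direction of any confounding cannot be determined from the documents. With history moderately commoner in the warfarin cohort, factors of about 0.84 to 0.96 on the recurrent VTE hazard ratio are illustrative, and a wide contrast gives 0.79. With equal prevalence there is no bias, and with history commoner in the apixaban cohort the direction reverses. These figures assume that history raises recurrence risk, differs between cohorts, and is not already captured by other covariates. No estimate is offered for discontinuation or switching.

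**What to change.** Add history of VTE to section 9.2.1, met by either of:

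- a personal-history-of-VTE code recorded before or during the index admission; or
- a VTE diagnosis code in any position in Dx or CDM, from all available data since 01 July 2017, dated before the index admission by at least a pre-specified gap.

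The gap is needed so that outpatient codes from the days leading into the index episode are not counted as history. Ordinary VTE codes from the index stay must not count, because the 6-month baseline contains that stay and nearly every patient would be flagged. A search limited to the 6 months before admission would do little: criteria 1 and 8 have already depleted that window, and older VTE would be missed.

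Report the variable by cohort. Force it, together with index year, into the recurrent VTE and discontinuation/switch models, exempt from backward elimination. Add to section 9.8 that VTE history is incompletely captured.

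The cost is one code list and one new covariate from sources already being linked; index year is already collected. The downside is small: the data before admission run from about 6 months (index 01 January 2018) to about 65 months (29 November 2022), so capture is unequal by index date and adjustment is partial.
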